5. PURPOSE AND STUDY OBJECTIVES

5.1 Purpose

The purpose of this study is to:

- Estimate the change in biomarkers of exposure (BOE) in adult smokers using VBM-FG2 versus adult smokers not using VBM-FG2.
- Determine the appropriate cigarettes per day (CPD) reporting method for baseline measurements (for interactive voice response system [IVRS] Base line is defined as the average CPD recorded on Days 2 through 8).

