5.3 Secondary Objectives

The secondary objectives of this study are to:

- Compare the difference in BOE (urinary total NNAL, nicotine metabolites, S-phenylmercaptmic acid [S-PMA], blood carboxyhemoglobin [COHb], and exhaled carbon monoxide [CO]) and CPD between two methods for determining CPD during the Baseline Period:
 - Recall of average daily CPD for prior week using Past 7 Day Cigarettes Use Questionnaire (Day I).
 - Daily CPD tracking using an IVRS (7 day average of values recorded on Days 2 through 8).
- Compare the differences in percent change in urinary nicotine equivalent (NE), S-PMA, blood COHb, exhaled CO, and CPD from Baseline to EOS between adult smokers randomly assigned to Test Group (*ad libitum* VBM-FG2 use) and Control Group (no VBM-FG2).
- Compare the changes in all BOE and CPD from Baseline to EOS between Test Group and Control Group over 4 weeks.
- Characterize subgroups based on change in CPD from Baseline to EOS (no change, <50% reduction, ≥50% reduction, 100% reduction, increase) within each study group.
- Characterize subgroups based on change in total NNAL from Baseline to EOS (no change, reduction, increase) within each study group.
- Compare changes in the Fagerstrom Test for Cigarette Dependence (FTCD) from Baseline (Day 8) to EOS within and between each study group.
- Compare changes on the Quit Attempts and Quitting Intentions from Baseline (Day I) to EOS within and between each study group.

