6. STUDY DESIGN

This is a randomized, controlled, open-label, parallel group, multi-center, 5-week pilot study to determine changes in BOE in adult smokers allowed *ad libitum* use of VBM-FG2 relative to adult smokers who are not allowed use of VBM-FG2. The data collected from this study will be used to estimate the variability of differences in the percent change from Baseline to the EOS in urinary total NNAL between Test and Control Groups; these findings will be used to estimate the sample size for a future pivotal study. This study will be conducted in approximately 150 adult

smokers who are considered to be in overall good health. Subjects will be randomized (based on gender, daily cigarette consumption [<20 and 20], and quit attempts [any quit attempts/no quit attempts]) to Test (allowed VBM-FG2 use) or Control (not allowed VBM-FG2 use) product in a 3:2 ratio (90 subjects randomized to Test: 60 subjects randomized to Control) with no more than a 60:40 distribution of either males or females to either group.

Screening	Baseline Period*		Product Use Period ^t			
Visit 1	Visit 2	Visit 3	Visit 4	Visit 5	Visit 6	Visit 7
Day -28 to Day -1	Day 1	Day 8±1	Day 15 ± 1	Day 22 ± 1	Day 29± 1	Day 36 ± 1
Subject evaluated against inclusion and exclusion criteria for study eligibility	Baseline CPD data gathered using recall of previous week and daily IVRS call.		Randomization in a 3:2 ratio (Test:Control) 
 • Test = ad libitum VBM-FG2 • Control = no VBM-FG2 			
Enrollment		Randomization				

*Baseline Period = after the daily IVRS call on Day 1 through the daily IVRS call on Day 8.

^t Product Use Period = after the daily IVRS call on Day 8 through the daily IVRS call on Day 36.

Note: Subjects in both groups are allowed to smoke their regular brand cigarettes during the entire study period

Expected duration of the study, from first subject first visit through last subject last visit is approximately 3 months. Expected duration for each subject is expected to be up to approximately 5 weeks (potentially 9 weeks from Screening to EOS). All subjects will be informed that they are allowed to smoke their own cigarettes or to quit smoking during the study.

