Screening (Visit 1) will occur within 28 days of Day 1 (Day -28 to Day -1). An informed Consent Form (ICF) must be signed prior to conducting any study related procedures. Potential subjects will undergo an initial evaluation (vital signs, urine pregnancy test [females only], and questionnaires) to determine initial eligibility. If the subject passes the initial evaluation, then he/she will be provided with a sample of VBM-FG2 and asked to use the product as they like for 15 minutes. Subjects will then complete a Potential Purchase Interest Questionnaire. If they indicate that they "definitely would buy" or "probably would buy" the product on the questionnaire, then the subject will undergo the rest of the screening procedures (clinical labs and electrocardiogram [ECG]). Laboratory values will be evaluated by a local laboratory.

Subjects will return to the study site on the evening of Day 1 for Visit 2. A physical examination will be conducted and subjects who satisfy all the inclusion criteria and exclusion criteria will be eligible for enrollment in the study. Once a subject is enrolled in the study (Day 1), if they choose to no longer participate, they will be considered a drop-out/early termination subject.

During the Baseline Period, at Visits 2 and 3 (Days 1 and 8), blood and urine samples will be collected for analysis of BOE. Subjects will also complete the Past 7 Day Cigarettes Use Questionnaire while at the study site, to indicate their CPD over the previous week. During the Baseline Period (Days 1 to 8) subjects will report CPD daily through an IVRS.

At Visit 3, approximately 150 subjects will be randomized to either the Test or Control Group in a 3:2 ratio (with not more than a 60:40 distribution of either males or females to either group). VBM-FG2 will be dispensed to subjects randomized to the Test Group for *ad libitum* use beginning after the Day 8 IVRS.

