11.4.2 Statistical Analyses of Secondary Endpoints

Difference in baseline:

Paired T Test will be used to examine the difference in all 5 BOEs between Day 1 and Day 8.

Paired T test will also be used to examine the differences in CPD between the once weekly recall at Day 8 (from questionnaire) and the average daily tracking of CPD from Days 2 through 8 (from IVRS).

Difference in change from baseline:

Linear mixed model for repeated measures analyses of variance will be used for the analyses of the secondary outcome measures: percent change from baseline and absolute change from baseline in all other BOEs. The same model will be used for percent change from baseline and absolute change from baseline in CPD and Total score of FTCD, the model details are as follows:

For other BOEs:

Model 1:

Percent (or absolute) change from baseline = study group + visit+ study group*visit + subject + random error

Model 2:

Percent (or absolute) change from baseline = study group+ visit+ study group*visit + subject + CPD + sex + race + BMI + age + random error

For CPD and Total Score ofFTCD:

Model 1:

Percent (or absolute) change from baseline = study group+ visit+ study group*visit +subject+ random error

Model 2:

Percent (or absolute) change from baseline = study group+ visit+ study group*visit +subject+ sex + race + BMI + age + random error

where

CPD = fixed effect covariate representing average number of cigarettes per day for the past two days from IVRS

study group = fixed effect term (test or control)

sex = fixed effect (male or female)

age = fixed effect covariate (continuous)

race= fixed effect (White or Non-White)

BMI = fixed effect covariate (continuous)

visit= fixed effect term representing days (ordinal categorical variable)

subject = random effect

baseline = Day 8 value for BOE and average of Day 2 to 8 for CPD (IVRS)

If the study group*visit interaction term is not statistically significant (P-value > 0.10), then the interaction term will be removed from the model and all comparisons will be done using the overall product means. If the interaction effect is significant (P-value < 0.10), then the comparisons will be conducted for each study visit.

Least squared mean and standard error for the product effect will be estimated by study group and visit with p-values for statistical significance. P-value will also be provided for other effects in the model.

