All secondary and exploratory analyses will be conducted on the Per-protocol population only.

A linear regression analysis will be conducted within each group at each timepoint to examine the relationships between levels of all 5 BOEs (dependent variable) with either weekly cigarette counts (Day 1 and 8 from questionnaire) or daily cigarette counts (from IVRS) (independent variable). For total NNAL, the corresponding daily cigarette counts from IVRS will be the average of past 7 days. For other biomarkers, it will be the average of past 2 days. The regression analysis will be conducted on the Per-protocol population.

The proportion of subjects in subgroups will be provided with proportion and sample size based on:

- 1) Cigarette consumption change from Baseline (average of Days 2 to 8 from IVRS) to the last week (no change, <50% reduction, 2::50% reduction , 100% reduction, increase);
- 2) Total NNAL change from Day 8 to the last visit (no change, reduction, increase);
- 3) Total scores of FTCD change from Day 8 to the last visit (increase, no change, decrease)
- 4) Proportion of subjects in subgroups based on Changes from Baseline (Day 1) to EOS (increase, no change, decrease) on the change in Quit Attempts from Day 1 to last visit.
- 5) Proportion of subjects in subgroups based on Changes from Baseline (Day 1) to EOS (yes to no, no to yes, and same) on the change in Quitting Intentions from Day 1 to last visit.

The Mantel-Haenszel Chi-Square Test will be used for (1), (2), (3), and (4); Fisher exact test will be used for (5) to test the frequency differences between the two groups.

Additional statistical analyses:

Wilcoxon signed rank test will be used to test the FTCD score difference between the 2 baseline measures (Visit 2 and 3) for the test group. If there is no statistical significance, the average score will be related to the average amount of VBM-FG2 in the past week via linear regression. Otherwise the FTCD score for Visit 3 will be used.

For the test group only, a simple linear regression model will be used to examine the relationship between COHb and Exhaled CO at each post-baseline visit.

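### Baseline CPD reporting method: the plan tests the mean difference between recall and IVRS but never contrasts how well each tracks exposure, and it splits the pre-product regressions by study group

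*SAP*

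**What the plan says.** SAP section 5.1 gives the study two purposes. The second is: "Determine the appropriate cigarettes per day (CPD) reporting method for baseline measurements". Section 5.3 turns this into a secondary objective, which compares BOE and CPD "between two methods for determining CPD during the Baseline Period". The two methods are a one-week recall questionnaire and daily IVRS tracking averaged over Days 2 to 8.

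Section 11.4.2 offers three analyses that bear on this:

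- **BOE across days.** "Paired T Test will be used to examine the difference in all 5 BOEs between Day 1 and Day 8". Section 11.3.2 presents this endpoint as weekly recall against daily tracking.
- **CPD by method.** A second paired t test compares Day 8 recall CPD with the IVRS average of Days 2 to 8. No split by group is stated.
- **BOE regressed on CPD.** "A linear regression analysis will be conducted within each group at each timepoint", relating each of the five BOEs "with either weekly cigarette counts (Day 1 and 8 from questionnaire) or daily cigarette counts (from IVRS) (independent variable"). For total NNAL the IVRS predictor is a 7-day average. "For other biomarkers, it will be the average of past 2 days". The population is Per-protocol.

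On timing, section 6 states: "Product Use Period = after the daily IVRS call on Day 8 through the daily IVRS call on Day 36". Randomization is 3:2, with 90 Test and 60 Control out of about 150.

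**The concern.** A reporting method is appropriate for baseline if its counts reflect what subjects smoke, and the BOEs are the study's objective evidence of that. The question therefore needs a comparison of how closely recall and IVRS each relate to exposure in the same subjects over the same days. The plan collects the data for this comparison but does not make it.

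The recall and IVRS regressions are run one predictor at a time and left side by side. They are divided by a group label that cannot yet have had a product effect. For four of the five BOEs the two predictors also cover different periods. A reader of the outputs would have to judge by eye between fits that differ in method and window, in two groups that may disagree.

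**Working it through.** **Inputs.** Section 6 gives about 150 subjects at 3:2: 150 × 3/5 = 90 and 150 × 2/5 = 60, which reproduces the stated group sizes. The SAP states no power, precision or correlation for this question. Every correlation below is an assumption, shown over a range.

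**1. What each planned analysis can show**

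| Analysis | What it compares | Shows which method tracks exposure? |
|---|---|---|
| Paired t test, BOE Day 1 vs Day 8 | Two days | No. A BOE level does not depend on how CPD was reported |
| Paired t test, CPD recall Day 8 vs IVRS Days 2-8 | Means of two methods | No. It tests mean difference only |
| Regressions of BOE on recall or IVRS | Each method with exposure, separately | Partly. The two fits are never contrasted |

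On the second row: if recall is unbiased on average but noisier than IVRS, the t test has nothing to detect, although recall tracks exposure less well. If recall differs from IVRS by a constant, the t test can be significant although both correlate equally with exposure.

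**2. Which timepoints allow a comparison.** Recall enters the regressions only at Days 1 and 8. IVRS reporting starts on Day 1, so no tracked week precedes Day 1. Only Day 8 allows a head-to-head comparison. Assigned product use begins after the Day 8 IVRS call, so every recall regression is split by a label that has not yet acted. At Day 8 the plan gives 5 BOEs × 2 methods × 2 groups = 20 fits. Pooled, there would be 5 × 2 = 10.

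**3. Precision of each fit.** With the same residual SD and spread of CPD in both groups, as randomization leads one to expect, the slope's standard error is proportional to 1/√n:

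- Test: √(150/90) = 1.29 times the pooled value.
- Control: √(150/60) = 1.58 times the pooled value.

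For a correlation, the 95% CI by Fisher's z is tanh(atanh r ± 1.96/√(n − 3)). For an assumed r = 0.4:

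- n = 60: 0.16 to 0.59
- n = 90: 0.21 to 0.56
- n = 150: 0.26 to 0.53

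Over assumed r from 0.2 to 0.6, the interval widths run from 0.49 down to 0.33 (n = 60), 0.40 to 0.27 (n = 90) and 0.31 to 0.21 (n = 150).

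**4. What a contrast of the two fits could achieve (illustrative).** This is the power of Williams' test for two dependent correlations, two-sided 5%, with 8,000 simulations per case and assumed BOE correlations of 0.4 and 0.3:

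| Assumed recall-IVRS correlation | n = 60 | n = 90 | n = 150 |
|---|---|---|---|
| 0.7 | 18% | 26% | 40% |
| 0.8 | 26% | 36% | 54% |
| 0.9 | 46% | 63% | 84% |

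**5. Can the groups disagree?** The same simulations, with recall-IVRS correlation 0.8 and then 0.9, give the share of trials in which Test and Control rank the methods in opposite order. It is about 35% and 26% for assumed correlations of 0.40 vs 0.35, and about 14% and 4% for 0.40 vs 0.30. The SAP has no rule for settling such a conflict.

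**6. Windows.** At Day 8, recall covers the past week. For total NNAL the IVRS average is also over 7 days. For nicotine equivalents, S-PMA, COHb and exhaled CO it covers 2 days, so any difference in fit mixes method with window.

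**The case against.** The strongest reply is that the plan does compare the methods. The paired t test of Day 8 recall against the IVRS average is a head-to-head in the same subjects over nominally the same week, and it matches the section 5.3 objective and the section 11.3.2 endpoint. It can be informative: at n = 150 its power is 68%, 86% and 95.5% for assumed standardized differences of 0.20, 0.25 and 0.30. This stands. A reader might infer that no statistic compares the methods, or that the purpose goes wholly unanswered. The document supports neither reading.

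Other replies also have force:

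- **Role of the regressions.** The SAP says only that they examine relationships. It does not say that they decide the method or that the pivotal study's choice rests on them. Sections 5.1 and 11.2 already set the IVRS Day 2-8 average as the CPD baseline. The narrower point remains that no other analysis links each method to exposure.
- **Precision.** The two groups are independent, so their results could be combined to recover essentially the pooled precision. The ratios 1.29 and 1.58 describe each separate fit, not information lost to the study. But the SAP plans no such combination.
- **Two-day window.** It is used consistently for the other BOEs, and section 11.2 ties the 7-day average to the longer half-life of NNAL. That justifies keeping it as a fit, but not as the only IVRS comparator to 7-day recall.
- **Day 1 vs Day 8 BOE test.** Section 11.2 expects tracking to change smoking, so the test is useful. Its label as a method contrast is what misleads.
- **Product exposure.** It would be wrong to say that no product is used before Day 8. At Screening, a subject passing the initial evaluation "then he/she will be provided with a sample of VBM-FG2 and asked to use the product as they like for 15 minutes". This precedes randomization and is unrelated to group, so the point concerns assigned use only.

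**Conclusion.** The concern holds in limited form. The plan addresses the choice of CPD reporting method through a test of mean difference, but has no statistic showing which method tracks exposure better. The regressions that come closest are split by group before the assigned product can act. Each fit's standard error is about 1.29 (Test) or 1.58 (Control) times that of a pooled fit. For four of five BOEs, method and time window are also confounded.

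The ratios assume that all 150 subjects are analysable and that residual SD and CPD spread are equal in the two groups. The Per-protocol restriction would make actual numbers smaller. The power and ranking figures are illustrative, because the SAP gives no correlations. This is a secondary improvement in a pilot and does not affect the primary NNAL comparison.

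**What to change.** In section 11.4.2:

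1. At Day 8, fit both groups together. Relate each of the five BOEs to Day 8 recall and, separately, to the IVRS average over Days 2 to 8, in the same subjects.
2. For each BOE, report the difference between the two dependent correlations (or R-squared values) with a 95% CI, for example by bootstrap over subjects.
3. Keep the 2-day IVRS average as a supplementary fit for the BOEs other than total NNAL.
4. Keep the planned paired t test of CPD.
5. Keep by-group regressions for post-baseline visits only.
6. In sections 11.3.2 and 11.4.2, describe the Day 1 vs Day 8 BOE test as a check on whether exposure changed during the tracking week.

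The cost is revised SAP wording and a short extra program. No new data are needed, the number of Day 8 regressions on matched windows falls from 20 to 10 before the supplementary fits, and the primary analysis is unchanged.

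### The Day 1 and Day 8 regressions of biomarker level on CPD are split by study group although product use has not begun, which costs precision in an analysis that bears on the choice of CPD reporting method

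*SAP*

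**What the plan says.** - **Analysis.** SAP section 11.4.2 plans: "A linear regression analysis will be conducted within each group at each timepoint to examine the relationships between levels of all 5 BOEs". The predictor is "either weekly cigarette counts (Day 1 and 8 from questionnaire) or daily cigarette counts (from IVRS) (independent variable"). For total NNAL the IVRS value is a 7-day average; for the other four biomarkers it is a 2-day average.
- **Population.** "The regression analysis will be conducted on the Per-protocol population".
- **Timing.** Section 6: "At Visit 3, approximately 150 subjects will be randomized to either the Test or Control Group in a 3:2 ratio". Visit 3 is Day 8. Product is handed out at that visit, for use after that day's IVRS call. Section 9.1 has urine collected on arrival. The only earlier exposure to the product is the 15-minute trial at Screening, before anyone is assigned.
- **Allocation.** Section 6: "90 subjects randomized to Test: 60 subjects randomized to Control".
- **Purpose served.** Section 5.1, second item: "Determine the appropriate cigarettes per day (CPD) reporting method for baseline measurements".
- **Other comparisons of the methods.** Section 11.4.2 also plans paired t tests of the five biomarkers (Day 1 against Day 8) and of CPD (Day 8 recall against the IVRS average of Days 2 to 8). No split by group is stated for these.

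**The concern.** Recall CPD enters only at Days 1 and 8. Every recall regression therefore precedes product use, and so does Day 8, the only timepoint at which recall and a full week of IVRS data exist together. At that stage the study group is a label for future treatment. A by-group fit has no group effect to estimate, and each fit discards the information in the other group.

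This matters because these are the only regressions in the SAP that set biomarker level against each of the two CPD methods. The paired t tests can show that the methods give different mean CPD, or that mean biomarker levels differ between Day 1 and Day 8. They cannot show which method tracks exposure more closely. As planned, the reader gets two slopes and two fits per biomarker and method, each less precise than necessary. No pooled result is planned, and no rule says what to conclude if the groups disagree.

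**Working it through.** **Inputs from the SAP.** About 150 randomized, 3:2 (section 6); separate fits by group (section 11.4.2). The SAP gives no biomarker-CPD correlation, no correlation between the two CPD methods, and no significance level for these regressions. Those used below are assumptions: biomarker-CPD correlation 0.2 to 0.5, correlation between methods 0.6 to 0.9, two-sided 5%.

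**Step 1. The plan's own figure.** 150 × 3/5 = 90 and 150 × 2/5 = 60. The stated split reproduces.

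**Step 2. Precision of the slope.** For the same CPD spread and residual SD, the standard error is proportional to 1/√n.
- Test: √(150/90) = 1.29 times the pooled standard error.
- Control: √(150/60) = 1.58 times.

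Per-protocol losses leave these ratios unchanged if the 3:2 split is kept. With 72 and 48, for example, √(120/72) = 1.29 and √(120/48) = 1.58.

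On the correlation scale, the 95% interval is tanh(atanh r ± 1.96/√(n−3)). At an assumed r = 0.4 this gives 0.26 to 0.53 pooled, 0.21 to 0.56 in Test and 0.16 to 0.59 in Control.

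**Step 3. Power to detect a nonzero correlation**, Φ(atanh r × √(n−3) − 1.96):

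| Assumed r | n = 150 | n = 90 | n = 60 |
|---|---|---|---|
| 0.2 | 69% | 47% | 33% |
| 0.3 | 96% | 82% | 65% |
| 0.4 | >99% | 98% | 89% |

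**Step 4. Can the groups rank the methods differently?** 20,000 trials were simulated with jointly normal biomarker, recall and IVRS values and no true group difference. In each, the method with the higher sample correlation was taken as the better one. That ranking rule is also an assumption, because the SAP gives none.

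| Correlation with biomarker (worse / better method) | Between methods | Better method ranked first: pooled | Test | Control | Groups disagree |
|---|---|---|---|---|---|
| 0.40 / 0.40 | 0.8 | – | – | – | 50% |
| 0.35 / 0.40 | 0.8 | 85% | 79% | 74% | 36% |
| 0.35 / 0.40 | 0.9 | 93% | 87% | 82% | 26% |
| 0.30 / 0.40 | 0.6 | 93% | 87% | 82% | 26% |
| 0.30 / 0.40 | 0.8 | 98% | 95% | 91% | 14% |
| 0.30 / 0.50 | 0.8 | 100% | >99% | >99% | 0.3% |

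The groups are independent, so disagreement can be checked by hand. For the second row, 0.789 × (1 − 0.742) + 0.742 × (1 − 0.789) = 0.204 + 0.157 = 0.36.

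**Step 5. Where the two methods can be compared.** Daily IVRS reporting starts in the Baseline Period, so Day 1 has no preceding IVRS week and supports a recall fit only. The direct comparison exists at Day 8. There the two methods cover a similar 7-day window for total NNAL only; for the other biomarkers a 2-day IVRS average is set against a 7-day recall. Pooling does not change that mismatch.

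**The case against.** The strongest reply is that the SAP nowhere makes these regressions decisive. Sections 5.3 and 11.3.2 define the comparison of methods as differences in biomarkers and CPD, which the paired t tests address without a stated split. The regressions are listed neither as an objective nor as an endpoint. Section 11.2 already fixes the IVRS average of Days 2 to 8 as the CPD baseline for change. All of this stands. A reader might infer that the choice of CPD method rests on two underpowered regressions, and the SAP does not support that.

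Nor are the by-group fits weak in every case. At a correlation of 0.4, power is 98% and 89%. Disagreement is common mainly when the methods perform alike, and then a wrong pick costs least. That stands too.

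By-group slopes could be combined afterwards, section 4 allows supplementary analyses, and a by-group Day 8 fit is a reasonable reference for the fits at Visits 4 to 7. This limits the harm but gives no reason to make the split the main baseline analysis. Per-protocol membership is settled after randomization, so the analysed groups are not strictly random subsets of one sample. That is no reason to split either.

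A reader might also see the same fault in the Wilcoxon test planned to "test the FTCD score difference between the 2 baseline measures (Visit 2 and 3) for the test group". The text does not bear this out. That test decides which FTCD score is regressed on VBM-FG2 use, and only the Test group is given the product. Restricting it to Test is coherent.

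**Conclusion.** The point holds as a loss of efficiency and clarity in a secondary analysis. Splitting the Day 1 and Day 8 fits by a label that cannot yet have an effect raises the slope standard error by about 29% in Test and 58% in Control. This rests only on the 90:60 split and on similar CPD spread and residual variance in the two groups. The split also allows contradictory rankings of recall and IVRS, with a chance from 0.3% to about 50% that depends wholly on assumed correlations. It introduces no bias and does not touch the primary NNAL comparison. The exact statement for Day 8 is that ad libitum use has not begun; product is dispensed at that same visit, so it would be wrong to say that none has been dispensed.

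**What to change.** In SAP section 11.4.2:
- Make the main Day 1 regression (recall only) and the main Day 8 regressions (recall and IVRS) single fits in both groups combined, in the Per-protocol population as now specified.
- Report one slope with confidence interval and one R-squared per biomarker and method.
- Keep the fits within each group for Visits 4 to 7, and show by-group Day 8 fits as supplementary reference.
- Leave the FTCD Wilcoxon test as it is.

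The cost is a few lines of SAP text and a small change to programs and table shells. No new data are needed.
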